3.2 Study Population

Male and female subjects age 55-79 years AND history of smoking. Population will be identified via local general population-based registries (“Einwohnermeldeämter”) and informed about the screening study by mail. The registries are general population based local registries (“Einwohnermeldeamt”), where all inhabitants in a region are registered by law. We requested Name, birthdate and address from the 3 participating cities (Hannover, Lübeck and Hamburg) in the age group 55-79. Additional recruitment efforts via local physicians (GPs, specialists) and campaigns targeting the general public.

Mailed information package will contain a response element (paper) with questions concerning their smoking habits and history and link to study website. Interested individuals might either reply using the response element or input their data on the study website. Self-reported health data will be used to pre-qualify subjects based on PLCO / NELSON criteria.

Subjects with preliminary PLCO risk-score $\geq 1.58\%$ (6 years) or NELSON inclusion criteria will be invited to one of the study centers (high-risk group). On site, all subjects will undergo validation of their risk scores, additional examination of their medical condition, medical history and current medication by qualified personnel. Data will be stored in specially designed database (Clinical Research Organisation – CRO).

Subjects, who did not meet the NELSON or PLCO criteria, will be asked to volunteer by contributing long-term outcome data, from regional and national cancer registries informing of the development of lung cancer or death from lung cancer (low-risk group).

Subjects included will be randomized prior to the initial LDCT scan. Randomization will not affect the procedure of the lung cancer screening protocol but only determine the participants

of the coronary calcium score and emphysema score reporting vs. non-reporting group. Randomization ratio of 1:1 and a 2-factorial design (1/4 calc score only; 1/4 emphysema score only, 1/4 both; 1/4 none) will provide equally sized groups of patients in the reporting and non-reporting group.

Randomization will be upheld for the one year CT screening round. Coronary calcium and emphysema scores of the subjects in the non-reporting group will remain confidential during the entire study duration (10 years).

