4.2 Outcomes

Primary endpoints:

1. Proportion of lung cancers detected with different risk models

To address the suitability of different inclusion methods for identifying the high-risk population for screening, the PLCO_M2012 model and the NELSON inclusion criteria will be compared primarily for the positive predictive value of lung cancers detected within the study population after 2 screening rounds.

Key-Secondary endpoints:

Additionally, the PLCO_M2012 model and the NELSON inclusion criteria will be compared in a hierarchical order regarding the key secondary endpoints:

1. Proportion of individuals selected for screening within the high-risk study population
2. Proportion of lung cancers detected with different inclusion methods (NELSON vs. PLCO) within the overall study population after 5 years
3. Proportion of lung cancers detected within the high-risk population
4. Sensitivity within the overall population after 5 years.

5. Specificity within the overall population after 5 years.

Secondary endpoints:

6. **Rate of initiation of cardiovascular treatments** (in particular lipid-lowering) in the calcium score reporting group vs. the non-reporting group after year 1 of study.
7. **Efficiency of nodule management algorithms:** Based on the two alternative management algorithms (LungRads1.1 alone or LungRads1.1 + PanCan/AI) participants are sorted into three management groups: (a) next surveillance scan, (b) early recall scan, or (c) diagnostic evaluation recommended. For one algorithm to be more efficient, the following criteria must both be fulfilled
 - i. The number of participants without cancer sorted in the category (a) is higher AND
 - ii. The number of participants with lung cancer sorted into category (b) or (c) is higher.
8. **Success of screening program.** Based on all individuals enrolled. Definition of success is calculated using:
 - a. Response rate (1. Respondents to questionnaire / invitation: those who send their smoking history & other relevant data; 2. among the above respondents, those who are eligible by one of the two criteria, or both; 3. those who are eligible, and actually take part in the screening), number of drop-outs, effectiveness of patient recruitment via mailings vs. GPs referrals (individual response rates)
 - b. Reliability of PLCO risk scoring (self-reported vs. on site assessment)

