For testing the null-hypothesis of no difference between the risk scores regarding the proportion of individuals selected for screening, McNemar's Test will be used.

Description of the primary analysis and population:

The primary analysis will be conducted of all volunteers within the overall study population after 2 LDCT screening rounds.

5.1.2 Secondary Objective(s): Calculation of Epidemiological Measure(s) of Interest (e.g. hazard ratios, incidence rates, test/retest reliability)

1. Rate/rate ratio of initiation of cardiovascular treatments (in particular lipid-lowering) in the calcium score reporting group vs. the non-reporting group after year 1 of study:

2. Efficiency of nodule management algorithms:

Based on the two alternative management algorithms (LungRads1.1 alone or LungRads1.1 + PanCan) patients are sorted into three management groups: (a) next surveillance scan, (b) early recall scan, or (c) diagnostic evaluation recommended. For one algorithm to be more efficient, the following criteria must both be fulfilled

- i. The number of patients without cancer sorted in the category (a) is higher AND
- ii. The number of patients with lung cancer sorted into category (b) or (c) is higher.

3. Success of screening program. Based on all individuals enrolled. Definition of success is calculated using:

a. Response rate (number of responses/overall number contacted), number of drop-outs, effectiveness of patient recruitment via mailings vs. GPs referrals (individual response rates)

b. Percentage of subjects meeting all inclusion/exclusion criteria

c. Repeatability of the PLCO score

d. Percentage of subjects receiving an adequate low-dose CT scan according to DRG guidelines (number of diagnostic CTs/number of all CTs)

4. Quality of screening program.

a. CT reading performance (2nd reader vs. CAD vs. AI)

b. Frequency of detection and management of incidental findings from low dose chest CT (emphysema, coronary heart disease, etc.)

c. Subsequent identification of biomarkers with predictive value / correlation with positive LDCT findings / cancer risk

5. Smoking cessation

a. Success of smoking cessation counseling based on number of participants quitting with or without revealing additional health risks (emphysema score, coronary calcium score or both).

6. Blood-based and exhalation- based biomarkers

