6.2.1 Subject Informed Consent

Before documentation of any data, informed consent (DZL broad consent) is obtained by the patient in writing.

An unconditional prerequisite for a patient participating in the study is his/her written informed consent. Adequate information must therefore be given to the subject by the investigator before informed consent is obtained. A person designated by the investigator may give the information, if permitted by local regulations. A patient information sheet in the local language will be provided for the purpose of obtaining informed consent. In addition to this written information, the investigator or his designate will inform the patient verbally. In doing so, the wording used will be chosen so that the information can be fully and readily understood by laypersons.

The patient information sheet will be revised whenever important new information becomes available that may be relevant to the consent of patients.

The written informed consent of the patient to participate in the clinical study has to be given before any study-related activities are carried out. It must be signed and personally dated by the patient and by the investigator / person designated by the investigator to conduct the informed consent discussion. Patients are also asked to give consent to additional analysis of tumor, blood or urine material. This approval is not a precondition for participation in the study.

Provision of consent will be confirmed in the CRF by the investigator. The signed and dated declaration of informed consent will remain at the investigator's site and must be safely archived by the investigator so that the forms can be retrieved at any time for monitoring, auditing and inspection purposes. A copy of the signed and dated information and consent should be provided to the subject prior to participation.

At any time during or after the HANSE study a volunteer can withdraw from the study without any reason. In this case all collected study data will be deleted.

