6.3 Management and Report of Adverse Events/Adverse Drug Reactions

6.3.1 Definition of Adverse Events (AE)

This is a population-based screening study without using medication. Low dose CT imaging will be conducted without use of contrast media, thus adverse drug reactions are not associated with the procedure. Once tissue sampling is recommended by the CT results possible adverse events due to a lung biopsy for example are part of the clinical routine workflow. Any adverse event that may have been caused by the imaging procedure or any follow-up procedure during the study will be captured and documented in the eCRF. Finally, after closure of the study, all documented events will be summarized in a line listing by the investigator.

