6.3.5 Reporting of Adverse Events

All SAEs will be reported, whether or not considered causally related to the study procedure(s). The reporting period for SAEs is the period immediately following the time that written informed consent until the end of the HANSE study (eCRF closure). The investigator is responsible for informing the Ethics Committee and/or the Regulatory Authority of the SAE as per local requirements.

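### Section 6.2.1 treats every withdrawal as erasure of all data, so formal withdrawals cannot be analysed by arm, eligibility cell, recruitment route or timing

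*Protocol*

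**What the plan says.** Protocol section 6.2.1 gives one route out of the study: "At any time during or after the HANSE study a volunteer can withdraw from the study without any reason". The consequence follows at once: "In this case all collected study data will be deleted". The section makes no exception for data gathered before withdrawal, for allocation, for safety records or for a count of withdrawals. It does require signed consent forms to be archived at the site and kept retrievable.

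Other sections rely on those data:

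- **Section 3.2:** "Subjects included will be randomized prior to the initial LDCT scan". Withdrawal can therefore follow allocation.
- **Section 4.2, item 8 (success of the programme):** the basis is "Based on all individuals enrolled", and the components include "number of drop-outs, effectiveness of patient recruitment via mailings vs. GPs referrals (individual response rates".
- **Section 5.1.1:** "The primary analysis will be conducted of all volunteers within the overall study population after 2 LDCT screening rounds".
- **Section 6.3.1 (eCRF records):** "Any adverse event that may have been caused by the imaging procedure or any follow-up procedure during the study will be captured and documented". A line listing of all documented events follows once the study closes.
- **Section 6.3.5:** "All SAEs will be reported, whether or not considered causally related to the study procedure(s".

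The synopsis allows for 10% drop-out by recruiting 5,500 to reach 5,000. It does not say how much of that is formal withdrawal and how much is missed visits or loss of contact.

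**The concern.** The rule merges two different decisions: not wanting further study procedures, and not wanting data already given to be used. A volunteer who only wants no second scan has no described way to leave without erasing the record.

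The statistical difficulty is that deletion happens after allocation and after results are known. The reporting arms receive a calcium or emphysema score, and some participants receive a suspicious scan. Either could prompt withdrawal. With the record gone, nobody can tabulate withdrawals by arm, eligibility cell, recruitment route or timing, and no sensitivity analysis can be built on their baseline data. A statistical analysis plan cannot repair this, because the data no longer exist.

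**Working it through.** **1. The sections side by side.** For a participant who formally withdraws after the first scan:

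| Commitment | Needs | Under 6.2.1 |
|---|---|---|
| 4.2 item 8: all enrolled, drop-outs, recruitment route | Enrolment record, route | Deleted; at most a bare count from archived consent forms |
| 5.1.1: all volunteers | PLCO/NELSON cell, cancer status | Deleted from numerator and denominator |
| Randomised reporting comparison | Allocation, outcome if already recorded | Deleted |
| 6.3.1: closing line listing | eCRF adverse events | Deleted |
| 6.3.5: SAE reporting | Notification to ethics committee or authority | A report already sent is not undone |

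The first four rows conflict with 6.2.1 as written. The fifth largely does not.

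**2. The plan's own power figure.** Inputs from section 5.3: 5,000 participants split 2,857 (both), 1,070 (NELSON only) and 1,072 (PLCO only). Cancer probabilities are (144/149)×(112/2857), (144/149)×(10/1070) and (144/149)×(27/1072). The test is the Kosinski weighted generalized score test, two-sided 5%. Simulation gives 80.1% (40,000 runs), against the stated 80.3%. The plan's figure reproduces.

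**3. Deletion unrelated to outcome (rates assumed).**

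- 10% lost from 5,500: 5,500×0.9 = 4,950 participants, about 142.5 cancers, power about 79–80%.
- 10% lost from 5,000: 4,500 participants, about 130 cancers, power about 75%.

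Within the planned allowance the loss of power is negligible.

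**4. Deletion related to having cancer, equal across cells (rates assumed).** With 2% of non-cases and 10%, 20% or 30% of cancers deleted from 5,000, power is about 76%, 71% or 65%. The expected PPV ratio hardly moves: on the expected table below it is 1.135 with 2% of non-cases and no cancers deleted, and 1.136 with 2% and 30%. This costs precision and does not bias the contrast.

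**5. Deletion that differs by cell (hypothetical).** Expected cancers: (144/149)×112 = 108.2, (144/149)×10 = 9.7 and (144/149)×27 = 26.1, rounded to 108, 10 and 26. The contrast rests on 10 + 26 = 36 discordant cancers.

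- PPV for PLCO = (108+26)/(2857+1072) = 134/3929 = 3.41%.
- PPV for NELSON = (108+10)/(2857+1070) = 118/3927 = 3.00%.
- Pooled p = 252/7856 = 0.03208.
- C = [108(1−p)² + 2749p²]/7856 = 0.01324.
- T = (difference in PPV)² / {[p(1−p) − 2C](1/3929 + 1/3927)} = 7.07, giving p = 0.008.

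Removing PLCO-only cancers completely, from numerator and denominator: five gives p = 0.047 and six gives p = 0.065. If only PLCO-only cancers are deleted, at 10%, 20% or 30% of 5,000, power is about 69%, 54% or 38%. These scenarios show sensitivity. Nothing in the protocol says that withdrawal would differ in this way.

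**6. Randomised comparison (hypothetical).** Suppose there is no true effect and 68% are treated among participants with coronary calcium. Suppose also that a fraction x of untreated participants in the reporting arm is deleted after the 1-year assessment. The apparent rate is 0.68/[0.68 + 0.32(1−x)]. At x = 5% it is 69.1%, a spurious 1.1 points; at x = 10% it is 70.2%, a spurious 2.2 points. The planned effect in this subgroup is 5 points.

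**The case against.** A reader might infer more than the text supports. Five points on the other side stand.

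- **That drop-outs become uncountable.** Archived consent forms offer a route to a bare count, and section 5.2.1 says recruitment pathways will be tracked. People who miss visits without withdrawing are drop-outs too, and their data are not deleted. What is lost is the breakdown of formal withdrawals.
- **That the 10% drop-out measures the deletion.** Taking 5,500×10% = 550 people and 144/5,000 = 2.88% gives 550×2.88% ≈ 16 cancers. That is what would be deleted if every drop-out were a formal withdrawal with the average cancer yield. It is not an estimate of deleted data.
- **That deletion causes most of any bias in the cardiovascular endpoint.** Treatment initiation is ascertained at the 1-year visit. Someone who withdraws before then has no outcome under any rule, so for them the problem is ordinary missing data. Retained baseline data would help with it but not remove it. Deletion adds lost outcomes only for later withdrawals. The protocol also treats the secondary parameters as exploratory (section 5.2.2).
- **That the primary contrast is biased.** It compares two PPVs in overlapping groups of the same participants. Cancer-related withdrawal at equal rates across cells leaves the ratio almost unchanged, and the protocol gives no reason to expect different rates by cell.
- **That SAE reporting is defeated.** Section 6.3.5 concerns notification, which later deletion does not reverse. The exposure is in the closing listing under 6.3.1.

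It is also fair to say that the consent forms are separate documents, and that whether data may be kept by default is partly a legal and ethical decision. That limits how the fix is worded. It does not remove the conflict, because an unconditional deletion rule is stated in the protocol itself.

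**Conclusion.** The point holds in a limited form. As written, 6.2.1 turns each formal withdrawal into irreversible loss of allocation, eligibility cell, any detected cancer and eCRF harms, and it is not reconciled with 4.2, 5.1.1 or 6.3.1. The size cannot be stated, because the protocol does not give the withdrawal share of the 10% drop-out. If deletion is unrelated to outcome, the allowance of 5,500 absorbs it, with power at about 79–80%. If it is related to arm, scan result or eligibility cell, a few records could matter: on the expected table, six PLCO-only cancers separate p = 0.008 from p = 0.065. That pattern is assumed and not predicted; the difficulty is that the rule removes the data needed to check for it. None of the protocol's stated figures is shown to be wrong. This is a cheap improvement to make and does not show that the primary analysis is invalid.

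**What to change.** In section 6.2.1 and the consent form, describe two separate choices:

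- **(a) Stopping further participation.** Data collected to date are kept and, where consent and law allow, registry follow-up continues.
- **(b) An explicit request for erasure.** This is honoured.

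For (b), keep a non-identifying tally by arm, PLCO/NELSON cell and recruitment route, as far as data protection permits. Then align 4.2 item 8, 5.1.1 and 6.3.1 with 6.2.1, so that each says how erased participants are counted or acknowledged.

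The cost is protocol and consent wording, with data-protection and ethics review. The remaining downside is that some data will still be lost to erasure requests, and small tally cells may have to be merged to stay non-identifying.

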6.2.2 Confidentiality of Study/Subject Data

All data collected in this study will be strictly confidential in accordance with all appropriate legislation. Access to the participant files will not be permitted to anyone other than the study staff, monitors and auditors. Only the study staff involved in data collection will know the identity of the participants. Study staff will be instructed to maintain complete confidentiality of all collected data. Patient files will be kept on secure servers. The study report will not contain any patient identifying information. Participants will be assigned a unique participant number to ensure confidentiality and anonymity. Interview transcripts will be identified by this unique participant number and will not have any identifiers associated with the individual.

6.3 Management and Report of Adverse Events/Adverse Drug Reactions

6.3.1 Definition of Adverse Events (AE)

This is a population-based screening study without using medication. Low dose CT imaging will be conducted without use of contrast media, thus adverse drug reactions are not associated with the procedure. Once tissue sampling is recommended by the CT results possible adverse events due to a lung biopsy for example are part of the clinical routine workflow. Any adverse event that may have been caused by the imaging procedure or any follow-up procedure during the study will be captured and documented in the eCRF. Finally, after closure of the study, all documented events will be summarized in a line listing by the investigator.

6.3.2 Definition of Serious Adverse Events (SAE)

A serious adverse event is an AE occurring during any study phase (i.e., run-in, treatment, washout, follow-up), that fulfils one or more of the following criteria:

- Results in death
- Is immediately life-threatening
- Requires in-patient hospitalisation or prolongation of existing hospitalisation
- Results in persistent or significant disability/incapacity or substantial disruption of the ability to conduct normal life functions

- Is a congenital abnormality or birth defect
- Is an important medical event that may jeopardise the subject or may require medical intervention to prevent one of the outcomes listed above.

6.3.3 Definition of Adverse Drug Reactions (ADR)

An ADR is the development of an undesirable medical condition or the deterioration of a pre-existing medical condition following or during exposure to a medicinal product, suspected to be causally related to the product.

6.3.4 Collection of Adverse Events

Record all AEs with a fatal outcome in the *eCRF*.

For each AE the following variables will be collected;

- AE (verbatim)
- The date when the AE started and stopped
- Whether the AE is serious or not
- Investigator causality rating against the medicinal product (yes or no)
- Action taken with regard to medicinal product
- Outcome

It is important to distinguish between serious and severe AEs. Severity is a measure of intensity whereas seriousness is defined by the criteria in Sections 6.3.1 to 6.3.3 above. An AE of severe intensity need not necessarily be considered serious. For example, nausea that persists for several hours may be considered severe nausea, but not a SAE unless it meets one of the criteria shown in Section 6.3.2. On the other hand, a stroke that results in only a limited degree of disability may be considered a mild stroke but would be a SAE if it satisfies one of the criteria shown in Section 6.3.2.

Any AE which is not required to be collected, as specified in the protocol, can be reported according to local regulations.

Causality collection

The Investigator will assess the causal relationship between study procedures and each Adverse Event, and answer 'yes' or 'no' to the question 'Do you consider that there is a reasonable possibility that the event may have been caused by the study procedure?'

Time period for collection of adverse events

Adverse Events will be collected from time of the 1st screening round visit *and during any follow-up period specified in the protocol*.

6.3.5 Reporting of Adverse Events

All SAEs will be reported, whether or not considered causally related to the study procedure(s). The reporting period for SAEs is the period immediately following the time that written informed consent until the end of the HANSE study (eCRF closure). The investigator is responsible for informing the Ethics Committee and/or the Regulatory Authority of the SAE as per local requirements.

